2.2.2.3 Background Clinical Experience With Amgen Investigational Product Tarlatamab

As of the 15 April 2021 data cutoff, 91 subjects were enrolled in the tarlatamab first-in-human (FIH) Study 20160323, 88 (96.7%) of whom received at least 1 dose of tarlatamab. Seventy subjects received monotherapy: 1 subject each was assigned 0.003, 0.01, 0.03, and 0.1 mg of tarlatamab; 12 subjects were assigned 0.3 mg; 8 subjects were assigned 1 mg; 11 subjects were assigned 1 to 3 mg; 10 subjects were assigned 1 to 10 mg; 8 subjects were assigned 1 to 30 mg; 13 subjects were assigned 1 to 100 mg; and 4 subjects were assigned 1 to 25 to 100 mg of tarlatamab monotherapy administered intravenously (IV) every 2 weeks (Q2W). Overall, all subjects (100%) had treatment emergent adverse events (TEAEs); the most commonly reported adverse events were cytokine release syndrome (31 subjects [44.3%]); pyrexia (22 subjects [31.4%]); fatigue (18 subjects [25.7%]); constipation (17 subjects [25.7%]); nausea (16 subjects [24%]); anemia (12 subjects [17.1%]); and dysgeusia and dyspnea (11 subjects each [15.7%]). Serious adverse events were reported for 33 subjects (47.1%), treatment related adverse events leading to withdrawal from tarlatamab were reported for 3 subjects (3%), and grade ≥ 3 treatment-emergent adverse events (TEAEs) were reported for 34 subjects (48.6%). One subject (1.4%), who received 2 doses of tarlatamab at 0.3 mg IV Q2W, had a treatment-emergent fatal adverse event of pneumonitis, which was considered to be a dose-limiting toxicity (DLT) event.

Cytokine release syndrome (CRS) is the most frequently reported adverse event occurring in 31 subjects (44.3%) with grade 2 CRS occurring in 7 subjects (10%) and grade 3 CRS occurring in 1 subject (1.4%). No grade 4 or higher CRS has been reported at the time of the data cutoff date. CRS presented mainly as fever, tachycardia, nausea and fatigue ± hypotension and was reversible. In 8 subjects (11.4%), CRS was reported as a serious adverse event, 1 event of which led to treatment discontinuation. CRS occurred predominantly following the first 2 doses of tarlatamab in cycle 1 (CRS typically did not recur in subsequent cycles following cycle 1), and was managed with supportive care and corticosteroids.

Based on emerging data, neutropenia has been reported in the FIH study. As of 28 July 2021, with a total of 113 subjects (112 subjects in Study 20160323 and 1 subject

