4.1 Overall Design

This is an open label phase 1b study evaluating tarlatamab monotherapy.

[figure not shown]
Tarlatamab will be administered as a short-term IV infusion Q2W (with step dosing) in a 28-day cycle as monotherapy therapy in subjects with de novo or treatment-emergent NEPC.

The study will consist of 2 parts: dose exploration (Part 1) and dose expansion (Part 2).

Dose Exploration (Part 1)

The dose exploration part of the study will enroll up to 20 subjects with relapsed/refractory (RR) NEPC. At the time of initiation of the study, the starting dose will be the highest dose deemed safe and tolerable in the ongoing phase 1 trial of tarlatamab in subjects with small cell lung cancer (Note: based on emerging safety data

from Study 20160323, the starting dose may be lower than the highest dose deemed safe and tolerable). The planned highest dose in this study is not anticipated to exceed the maximum tolerated dose (MTD) as established in the ongoing Study 20160323. Based on results from study 20160323 in small cell lung cancer, the doses that may be explored in this study are presented in [Table 4-1](#).

Due to its known mechanism of action, subjects are at an increased risk for first dose effects (eg, CRS with associated manifestations and any other potentially evolving and unknown first dose effects) following the initial infusion of tarlatamab. To mitigate these risks, a step dosing approach will be implemented. One of the following step dosing approaches will be utilized as the initial dosing schedule based on emerging data and the dosing schedule associated with the highest dose deemed safe and tolerable from the ongoing first-in-human (FIH) study (Note: based on emerging safety data from Study 20160323, the starting dose may be lower than the highest dose deemed safe and tolerable).

- Single-step dosing involving a run-in dose on day 1, followed by a step dose on day 8 (equal to the target dose) and the target dose on day 15 then Q2W.

Based on emerging safety, pharmacokinetic and pharmacodynamic data from this study as well as the ongoing FIH study (20160323) and the recommendations of the DLRT, multiple or parallel dosing cohorts may also be opened simultaneously to assess any of the step-dosing strategies as described above.

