If late onset adverse events occur during a cohort, the DLRT may adaptively re-consider the doses evaluated within a cohort for subsequent dosing and/or possibly trigger a de-escalation or withholding of additional doses in subsequent cohorts. The maximum tolerated dose (MTD) will be estimated using isotonic regression (Ji et al, 2010) and the MTD will be the dose level with the estimated DLT rate closest to 0.30. In order to consider a certain dose Level as the MTD at least 6 DLT evaluable subjects must be enrolled at that dose level. No more than 10 DLT evaluable subjects will be enrolled at any specific dose level in dose exploration phase.

Dose exploration phase will end once any of the following events occur:

- Highest planned dose level is determined to be safe and tolerable (minimum of 6 evaluable subjects overall).
- Either Dose Level 1, 2 or 3 is determined to be safe and tolerable (minimum of 6 evaluable subjects) and the next higher dose level is determined to be unsafe and intolerable.

- All planned dose levels (including any intermediate doses or alternate dosing schedules) are determined to be unsafe and intolerable
- DLRT may decide to explore higher dose levels if it is deemed safe and the MTD is not reached at the highest dose planned.
- On the basis of a review of real-time safety data and available preliminary PK data, dose escalation may be halted or modified by the Sponsor as deemed appropriate.

The planned highest dose in this study is not anticipated to exceed the MTD as established in the ongoing Study 20160323.

At the time of enrollment, the dose-escalation phase (Part 1) will be eliminated if the recommended phase 2 dose (RP2D) has been selected in the ongoing phase 1 trial of tarlatamab in small cell lung cancer. Tarlatamab will then be dosed based upon the RP2D selected in the phase 1 trial in small cell lung cancer. Note: if Part 1 is initially eliminated based upon the RP2D selection in the phase 1 trial in small cell lung cancer, dose escalation may be opened in the future to explore additional dose(s) and dosing schedule(s) as described above.

Dose Exploration (Part 1)

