3.1 Study Design

This is an open label phase 1b study evaluating tarlatamab monotherapy. Tarlatamab will be administered as a short-term intravenous (IV) infusion every 2 weeks (Q2W) (with step dosing) in a 28-day cycle as monotherapy in subjects with de novo or treatment-emergent Neuroendocrine Prostate Cancer (NEPC).

The study will consist of 2 parts: dose exploration (Part 1), dose expansion (Part 2,

Dose Exploration (Part 1)

The dose exploration part of the study will enroll up to 20 subjects with relapsed/refractory NEPC. At the time of initiation of the study, the starting dose will be the highest dose deemed safe and tolerable in the ongoing phase 1 trial of tarlatamab in subjects with Small Cell Lung Cancer (SCLC) (Note: based on emerging safety data from Study 20160323, the starting dose may be lower than the highest dose deemed safe and tolerable). The planned highest dose in this study is not anticipated to exceed the maximum tolerated dose (MTD) as established in the ongoing Study 20160323.

Dose exploration will begin with treating 3 to 4 subjects at the Dose Level 1. The study dose limiting toxicity (DLT) period is 28 days. Once all subjects enrolled at a certain dose level are DLT evaluable, a dose level review team (DLRT) will convene. For any dose level, and depending on observed safety data, the following recommendation may occur:

- dose de-escalation to the next lowest dose level
- additional enrollment to the current dose level
- dose escalation to the next highest dose level

Dose escalation/de-escalation recommendations will be guided by a modified toxicity probability interval design (mTPI-2) model (Guo et al, 2017) with a target toxicity probability of 0.3 (protocol Table 4-2) and equivalence toxicity interval of (25%, 33%). The operating characteristics in protocol Table 4-3 provide the probability of selecting each dose level and the expected number of treated patients at each dose level for given hypothetical true DLT rates.

If late onset of adverse events occur during a cohort, the DLRT may adaptively re-consider the doses evaluated within a cohort for subsequent dosing and/or possibly trigger a de-

Date: 24 March 2023 Page 15 of 53

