escalation or withholding of additional doses in subsequent cohorts. The MTD will be estimated using isotonic regression (Ji et al, 2010) and the MTD will be the dose level with the estimated DLT rate closest to 0.30. In order to consider a certain Dose Level as the MTD at least 6 DLT evaluable subjects must be enrolled at that dose level. No more than 10 DLT evaluable subjects will be enrolled at any specific dose level in dose exploration phase.

At the time of enrollment, the dose-escalation phase (Part 1) will be eliminated if the recommended phase 2 dose (RP2D) or MTD has been selected in the ongoing phase 1 trial of tarlatamab in small cell lung cancer. Tarlatamab will then be dosed based upon the RP2D/MTD selected in small cell lung cancer trials. Note: if Part 1 is initially eliminated based upon the RP2D/MTD selection in the phase 1 trial in small cell lung cancer, dose escalation may be opened in the future to explore additional dose(s) and dosing schedule(s) as described above.

Dose Expansion (Part 2)

Once the RP2D/MTD has been determined, enrollment will commence in the dose expansion phase to confirm the safety and tolerability of the selected dose and to further evaluate anti-tumor activity.

One or more dosing schedules as described in Part 1 may be pursued in parallel during the expansion phase. Dosing schedules involving as noted in protocol Table 1-3 may be pursued in parallel or instead of the step dosing approach based on recommendations from the emerging safety, efficacy, and PK/PD data from the ongoing phase 1 trial in SCLC.

Based on emerging data from the tarlatamab monotherapy in this indication and emerging data from other trials with tarlatamab, the protocol may be amended to include a combination of tarlatamab with anti-PD-1 (L1) agent.

The overall study design is described by a study schema in protocol section 1.2.

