For subjects who discontinued treatment for any reason other than progressive disease, every effort should be made to perform radiographic imaging (CT/MRI/bone scintigraphy) of the chest, abdomen, pelvis, bone, and all other known sites of disease every 3 months until documentation of disease progression per PCWG3 guidelines, clinical progression, start of new anticancer therapy, or up to 3 years after the last dose of tarlatamab, whichever occurs first.

Treatment-related serious adverse events and fatal serious adverse events regardless of the cause should be collected during long-term follow-up.

Percent Change from Baseline

Percent change from baseline is calculated using the following formula:

Percent change from baseline = [(post-baseline value - baseline value) / baseline

value] x 100

Relative Dose Intensity

Relative dose intensity is calculated using the following formula:

Relative dose intensity (%) = (Actual cumulative dose / Planned cumulative dose) x 100; where actual cumulative dose = sum of received doses, planned cumulative dose = planned dose accumulated over the actual treatment duration, i.e., 100 mg x (number of records in exposure dataset - 1) + 1 mg. Actual and planned cumulative dose up to the study visit are considered.

Safety Follow-up (SFU)

Upon permanent discontinuation from the study treatment for any reason to further assess the risk of delayed adverse events, a SFU visit will be performed approximately 42 (+ 5) days after the end of the last dose of tarlatamab.

Date: 24 March 2023 Page 20 of 53

Study Day

If the date is after the date of study day 1, then study day is calculated as following:

Study day = (date - date of study day 1) + 1

If the date is before the date of study day 1, then study day is calculated as following:

Study day = (date – date of **s**tudy **d**ay 1)

Study Day 1

Study Day 1 is defined as the date of the first dose of tarlatamab administration to the subject.

Treatment Duration

Treatment duration is calculated using the following formula:

Treatment duration (weeks) = (last dose **date** – first dose **date** + 1) / 7.

5.2 Primary Endpoint-related Definitions

Dose-Limiting Toxicity (DLT)

DLT is defined as any qualifying toxicity that is at least possibly related to tarlatamab with an onset within the first 28 days following first dose with either of the following criteria:

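### SAP 5.1 hard-codes planned cumulative dose at 1 mg then 100 mg for every subject, so relative dose intensity is wrong for compliant subjects on any other regimen the design permits

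*SAP*

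**What the plan says.** SAP 5.1 (General Definitions, Relative Dose Intensity) divides the sum of doses received by the planned cumulative dose. It first describes the denominator in words, as "planned dose accumulated over the actual treatment duration". It then equates that, with an 'i.e.', to "100 mg x (number of records in exposure dataset - 1) + 1 mg". The formula has no term for dose level, schedule or study part, and nothing limits it to one regimen.

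The design that it serves is broader:

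- SAP 3.1, Part 1, allows both "dose escalation to the next highest dose level" and "dose de-escalation to the next lowest dose level".
- Protocol 4.1 lists, among the events that end dose exploration, "Either Dose Level 1, 2 or 3 is determined to be safe and tolerable" with the next higher level not tolerated. It also lets the review team go above the highest planned dose.
- Protocol 4.3 allows intermediate dose levels. Protocol 6.2.2.1.4 allows intra-subject escalation in Part 1.
- SAP 3.1, Part 2: "One or more dosing schedules as described in Part 1 may be pursued in parallel during the expansion phase". It adds that other schedules may be used alongside or in place of step dosing.

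Relative dose intensity is one of four exposure summaries in SAP 9.6.8. SAP 9.1 splits analyses by study part and, in Part 2, by group, unless otherwise specified. Protocol 9.4.2.1 asks for descriptive statistics by dose and dose schedule as appropriate.

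**The concern.** Relative dose intensity should show how much of his own planned treatment a subject received. A constant denominator does that only for subjects whose plan matches the constants. For anyone else, the value mixes delivery of treatment with the difference between the assigned regimen and 1 mg then 100 mg.

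At stake is how an exposure table reads. A lower dose level at which every dose was given would look poorly delivered. A summary by study part would then average such values with correct ones. Nothing in the formula would show whether a low value came from missed or reduced doses or from the assignment itself.

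**Working it through.** **Inputs**

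- Planned cumulative dose with n exposure records: P(n) = 100 × (n − 1) + 1 mg (SAP 5.1).
- Single-step schedule (protocol 4.1): the first, lower infusion is "followed by a step dose on day 8 (equal to the target dose) and the target dose on day 15 then Q2W". This is one low dose, then n − 1 target doses.
- This study's own dose levels are not visible in protocol Table 4-1 or section 4.3. As an assumption, I use regimens that protocol 2.2.2.3 reports for the first-in-human study: "8 subjects were assigned 1 to 30 mg; 13 subjects were assigned 1 to 100 mg", with 1 to 10 mg and 1 to 25 to 100 mg also listed there. The 200 mg target is purely hypothetical and only shows the direction of error above 100 mg.
- Every subject is taken as fully compliant, with one record per dose. The correct answer is therefore 100% throughout.

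The documents state no relative dose intensity value to reproduce.

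**Check on the encoded regimen.** For 1 mg then 100 mg, received dose is 1 + 100(n − 1) = P(n), so the result is 100% at every n. The formula is exact for this regimen.

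**Single step to a target T.** Result = [1 + T(n − 1)] / [1 + 100(n − 1)], which tends to T/100 as n grows. At n = 7, P = 601:

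- 1 to 10 mg: (1 + 6 × 10)/601 = 61/601 = 10.1%
- 1 to 30 mg: (1 + 6 × 30)/601 = 181/601 = 30.1%

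These do not recover with follow-up. At n = 13 they are 121/1201 = 10.1% and 361/1201 = 30.1%.

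**Extra step, 1 to 25 to 100 mg.** The second dose is 25 mg where the formula expects 100 mg, so the shortfall is a fixed 75 mg. Result = 1 − 75/P(n):

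| Doses | Received / P(n) | Result |
|---|---|---|
| 3 | 126/201 | 62.7% |
| 7 | 526/601 | 87.5% |
| 13 | 1126/1201 | 93.8% |
| 27 | 2526/2601 | 97.1% |

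**Target above 100 mg.** For the hypothetical 1 to 200 mg at n = 13: (1 + 12 × 200)/1201 = 2401/1201 = 199.9%.

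**Effect of pooling.** If equal numbers of compliant subjects received 7 doses of 1 to 30 mg and of 1 to 100 mg, the pooled mean would be (30.1 + 100)/2 = 65.1%.

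**Corrected denominator.** With each subject's own assigned doses as the denominator, all the cases above return 100%.

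**What the correction changes for 1 mg then 100 mg subjects.** With one record per scheduled dose, nothing. If missed doses leave no record, a subject who misses three 100 mg doses of 13 scheduled now gets 901/901 = 100%. Counting scheduled administrations gives 901/1201 = 75.0%. If an interrupted infusion creates two records, a compliant 13-dose subject now gets 1201/1301 = 92.3% and would get 100%.

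**The case against.** The strongest reply is that the constants may describe the only regimen in use. Protocol 4.1 and SAP 3.1 drop Part 1 if a dose has already been selected in the small cell lung cancer study. The only schedule set out in the current protocol 4.1, and the only cycle 1 table, is single-step. The SAP is dated March 2023, after dosing had begun (protocol 2.2.2.3 counts one exposed subject by July 2021), so its authors may have known the regimen. This stands as a limit on harm. It does not rescue the definition: the same SAP keeps dose exploration and parallel schedules open, and the protocol's partly blacked-out wording on step doses does not settle the matter.

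A second reply is that number of doses, cumulative dose and treatment duration are reported alongside, so a value near 10% with a full dose count would look odd. Protocol 9.4.2.1 also calls for summaries by dose and schedule, and SAP section 10 lists no departure from that. Both points help a careful reader notice the problem, but the value would still be wrong.

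A reader might go further and infer that every other regimen is badly understated. The arithmetic does not support that: the extra-step shortfall fades, and a target above 100 mg is overstated. Nor does the measure simply equal assigned dose over 100 mg. The numerator is dose received, so reductions still lower it.

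**Conclusion.** The definition holds for one regimen and is wrong for others that the documents permit. The error is large and persistent for targets below 100 mg, modest and fading for an added step that still reaches 100 mg, and upward for targets above 100 mg. Upward error is the least likely case, because protocol 4.1 does not anticipate exceeding the MTD of the first-in-human study.

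Two conditions apply. The percentages use another study's regimens as illustrations, because this study's doses are not visible. And if every subject is assigned 1 mg then 100 mg, the constants misreport no compliant subject. The documents do not show that anyone has been misreported.

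It would also be tempting to say that the error could distort the choice of RP2D. The documents do not support that. The MTD comes from DLTs through mTPI-2 and isotonic regression (SAP 3.3), and the dose level review looks at administration data directly (protocol Appendix 3). Relative dose intensity is a descriptive summary, neither a primary nor a secondary endpoint. The point is worth correcting because the rule is prespecified and the correction is small.

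**What to change.** In SAP 5.1, replace the constants. Define planned cumulative dose as the sum of the subject's own protocol-assigned planned doses at each scheduled administration over the actual treatment duration:

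- Use the run-in, step and target doses of his assigned dose level and schedule.
- Update the plan from the date of any approved intra-subject escalation. A plan frozen at enrollment would put an escalated subject above 100%.
- Do not update it for toxicity-driven reductions, so that these continue to lower the value.

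In SAP 9.6.8, summarise relative dose intensity by assigned dose level and schedule, in line with protocol 9.4.2.1.

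The cost is a short wording change and the matching programming. It needs each subject's assigned regimen, the date of any approved escalation and the scheduled administrations. Because scheduled administrations replace the record count, values for 1 mg then 100 mg subjects can change where doses were missed or records split. The SAP should say so. The change is to the analysis only and has no bearing on which doses are given.

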6.2.1.2.1 Dose Limiting Toxicity

Dose-limiting toxicity (DLT) is defined as any qualifying toxicity that is at least possibly related to tarlatamab with an onset within the first 28 days following first dose with either of the following criteria:

- Grade 3 adverse event lasting more than 3 days (with the exception of fatigue and Grade 3 non-febrile neutropenia that improves to \leq Grade 1 within 3 weeks including the use of growth factor support per neutropenia management guidelines [see Section 6.8.6]);
- \geq Grade 4 adverse event regardless of duration (with the exception of grade 4 non-febrile neutropenia lasting less than or equal to 7 days including the use of growth factor support per neutropenia management guidelines [see Section 6.8.6]).

Laboratory parameters of Grade 4, not considered clinically relevant and improved to Grade \leq 2 within 72 hours, will not be considered DLT's.

Asymptomatic grade 4 electrolyte abnormalities that last $<$ 72 hours, are not clinically complicated, and resolve spontaneously or respond to conventional medical interventions will not be considered DLTs.

The following adverse events will NOT be adjudicated as DLT regardless of the grade or duration:

- Lymphopenia
- Fever
- Tumor lysis syndrome (TLS) including associated manifestations attributable to TLS (eg, electrolyte abnormalities, renal dysfunction, hyperuricemia)

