6.2.2.1.3 Rules for Withholding or Restarting

Tarlatamab should be withheld for any of the following:

- DLT
- Symptomatic hypophysitis (See Section 6.8.3)
- Criteria for conditional withholding of tarlatamab due to potential hepatotoxicity (Section 6.2.3)

Tarlatamab dosing can be resumed if the toxicities resolve to grade ≤ 1 or return to subjects' baseline values within 4 weeks. The restarting of therapy should be deemed safe by the investigator and medical monitor.

Subjects should not be restarted with tarlatamab if the following treatment-related adverse events occur:

- Any grade ≥ 4 adverse events except those not considered DLT as described in Section 6.2.1.2.2
- Grade 3 adverse event(s) that do not recover to Grade 0-1 within 4 weeks
- Any grade 3 adverse events that recur (with the exception of grade 3 laboratory parameters not considered clinically relevant or recurrent non-febrile grade 3 neutropenia which resolves with supportive care to grade ≤ 1 or returns to subjects' baseline values within 4 weeks)
- Criteria for permanent withholding of tarlatamab due to potential hepatotoxicity (Section 6.2.3)

For adverse events related to CRS, neurological events and pituitary dysfunction, please see Sections 6.8.1, 6.8.2, and 6.8.3 respectively for guidelines for withholding and restarting criteria to pause enrollment.

At any point during the study, enrollment will be paused at the occurrence of 2 or more Grade 4 or one or more Grade 5 IP related adverse events. DLRT will be reconvened to review the safety data and determine appropriate next step that may include but not limited to implementing safety/toxicity management, informing health authorities, voluntarily putting the clinical trial on hold, or proceeding with enrollment (note: following the occurrence of an enrollment pause and DLRT review, a subsequent enrollment pause will occur at the occurrence of 2 or more new Grade 4 or one or more Grade 5 IP

related adverse events; additionally, if a pause and a DLRT has already occurred and the appropriate safety/toxicity management for Grade 4 adverse events have already been implemented a subsequent enrollment pause may not occur).

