8.2.5 Clinical Laboratory Assessments

Refer to Section 11.2 for the list of clinical laboratory tests to be performed and to the Schedule of Activities (Section 1.3) for the timing and frequency.

The investigator is responsible for reviewing laboratory test results and recording any clinically relevant changes occurring during the study in the Events CRF. The investigator must determine whether an abnormal value in an individual study subject represents a clinically significant change from the subject's baseline values. In general, abnormal laboratory findings without clinical significance (based on the investigator's judgment) are not to be recorded as adverse events. However, laboratory value changes that require treatment or adjustment in current therapy are considered adverse events. Where applicable, clinical sequelae (not the laboratory abnormality) are to be recorded as the adverse event.

All protocol-required laboratory assessments, as defined in Section 11.2, must be conducted in accordance with the laboratory manual and the Schedule of Activities (Section 1.3).

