- Grade 3 adverse event lasting more than 3 days (with the exception of fatigue and grade 3 non-febrile neutropenia that improves to ≤ grade 1 within 3 weeks including the use of growth factor support per neutropenia management guidelines [protocol Section 6.8.6]);
- ≥ Grade 4 adverse event regardless of duration (with the exception of grade 4 non-febrile neutropenia lasting less than or equal to 7 days including the use of growth factor support per neutropenia management guidelines [protocol Section 6.8.6]).
- Grade 5 adverse event

Laboratory parameters of Grade 3 or 4 of any duration, not considered clinically relevant, will not be considered DLTs.

Grade 4 electrolyte abnormalities that last < 72 hours, are not clinically complicated, and resolve spontaneously or respond to conventional medical interventions will not be considered DLTs.

Date: 24 March 2023 Page 21 of 53

The following adverse events will NOT be adjudicated as DLT regardless of the grade or duration:

- Lymphopenia
- Fever
- Tumor lysis syndrome (TLS) including associated manifestations attributable to TLS (e.g., electrolyte abnormalities, renal dysfunction, hyperuricemia)

DLT Evaluable

The DLT endpoint is evaluable if either: 1) the subject experiences a DLT, or 2) the subject does not experience a DLT and receives IP as planned in cycle 1 and has been followed for safety events a minimum of 28 days from start of treatment.

Maximum Tolerated Dose (MTD)

The MTD will be selected from all tried dose levels that have not been previously declared to be unsafe with a decision according to the mTPI decision table. The MTD will be estimated using isotonic regression (Ji et al, 2010) and the MTD will be the dose level with the estimated DLT rate closest to 0.30.

Treatment-Emergent Adverse Event (TEAE)

TEAE is defined as adverse events starting on or after first dose of tarlatamab as determined by "Did event start before first dose of investigational product" equal to "No" or missing on the Events CRF, and up to and including 47 days after the last dose of tarlatamab excluding the events reported after End of Study date.

Treatment-related Adverse Event (TRAE)

TRAE is defined as treatment-emergent AE that per investigator review has a reasonable possibility of being caused by **tarlatamab** as indicated on the Events CRF page.

5.3 Secondary Endpoint-related Definitions

Best Overall Response (BOR) per RECIST 1.1

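### SAP 5.2 exempts more laboratory events from DLT, a primary endpoint, than the current protocol does, so on the same subjects its DLT incidence can be lower but never higher

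*SAP*

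**What the plan says.** Both documents list DLTs as the primary endpoint for the MTD/RP2D objective (protocol section 3, SAP 2.1). Both use a 28-day window, at least possible relatedness, Grade 3 events lasting more than 3 days, and Grade 4 or higher events. The neutropenia exceptions and the terms that are never DLTs (lymphopenia, fever, tumor lysis syndrome) also match.

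The laboratory exemptions do not match. SAP 5.2 reads: "Laboratory parameters of Grade 3 or 4 of any duration, not considered clinically relevant, will not be considered DLTs". The protocol clause begins "Laboratory parameters of Grade 4, not considered clinically relevant and improved to Grade" and requires improvement to Grade 2 or lower within 72 hours. It has no general exemption for Grade 3 laboratory values. The protocol's electrolyte clause begins "Asymptomatic grade 4 electrolyte abnormalities that last" and sets a limit of under 72 hours. The SAP has the same clause without the restriction to asymptomatic events.

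Three other provisions bear on the point:

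- **Withholding.** Protocol 6.2.2.1.3 opens with "Tarlatamab should be withheld for any of the following" and lists DLT first.
- **Evaluability.** Without a DLT, a subject is DLT evaluable under SAP 5.2 only if "the subject does not experience a DLT and receives IP as planned in cycle 1" and 28 days of safety follow-up is complete. The protocol rule is equivalent.
- **Adverse event recording.** Under protocol 8.2.5, "abnormal laboratory findings without clinical significance" are in general not recorded as adverse events, but "laboratory value changes that require treatment or adjustment in current therapy are considered adverse events".

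The SAP states that it was written for Amendment 6 (29 September 2022). The protocol supplied is Amendment 7 (21 June 2024). SAP section 10, on changes from protocol-specified analyses, does not mention the DLT definition.

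**The concern.** Two rules for one primary endpoint mean that the same data can give two DLT counts. The SAP is the document that programmers follow, and its rule is the one more favourable to the drug. Consider a related laboratory adverse event judged not clinically relevant that is Grade 3 for more than 3 days, or Grade 4 and not down to Grade 2 by 72 hours. It is a DLT under the current protocol and not under the SAP.

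The protocol itself recognises this class of event. Its bar on restarting covers "Any grade 3 adverse events that recur (with the exception of grade 3 laboratory parameters not considered clinically relevant", so Grade 3 laboratory events of this kind are excused there, but the DLT definition does not excuse them.

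At stake is the reported DLT incidence. SAP 6.7.1 tabulates it for each part, and protocol 4.1 says the final MTD or RP2D estimate uses data from both parts. If more than one dose level is explored and a count sits on a boundary, the dose decision is at stake too.

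**Working it through.** **1. The plan's own figures.** Protocol 9.2 and SAP 3.2 give the probability of at least one DLT at true rates of 10% and 33%. The formula is 1 − (1 − p)^n:

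| n | p = 10% | p = 33% | Stated |
|---|---|---|---|
| 3 | 27.1% | 69.9% | 27% to 70% |
| 4 | 34.4% | 79.8% | 34% to 80% |
| 6 | 46.9% | 91.0% | 47% to 91% |
| 10 | 65.1% | 98.2% | 65% to 98% |

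All reproduce. Protocol Table 4-2 also reproduces in full under mTPI-2 with interval 25% to 35%, the 95% unsafe rule and a Beta(1,1) prior (assumed; none is stated for mTPI-2). These figures check the framework. They do not depend on which DLT definition is used.

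**2. Clause by clause.**

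| Clause | Protocol 6.2.1.2.1 | SAP 5.2 | Effect of SAP |
|---|---|---|---|
| Laboratory, not clinically relevant | Grade 4 only, and Grade 2 or lower within 72 h | Grade 3 or 4, any duration | Exempts more |
| Grade 4 electrolytes under 72 h, uncomplicated, resolving or treatable | Asymptomatic only | No such limit | Exempts more |
| Grade 5 | Within Grade 4 or higher | Listed separately as well | None |

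Each protocol exemption lies inside the matching SAP exemption and everything else is equal, so SAP DLTs are a subset of protocol DLTs. As a check, both rules were applied to all 4,608 admissible combinations of grade, duration, laboratory or electrolyte type, relevance, recovery, symptoms, complication and exceptions. The results were 1,072 DLT under both, 100 under the protocol only, 0 under the SAP only and 3,436 under neither. These are counts of logical cases, not frequencies.

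**3. Size per exempted event.** If the subject has no other DLT and n is unchanged, incidence falls by 1/n: 100/6 = 16.7 points, 100/10 = 10.0 points (10 is the Part 1 maximum per dose level) and 100/40 = 2.5 points (one Part 2 group of 40, all evaluable).

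**4. Denominator.** If cycle 1 dosing was withheld for the event, the subject has no SAP DLT and did not receive treatment as planned, so drops out of the DLT Analysis Set. Then 2/6 (33%) becomes 1/5 (20%) rather than 1/6 (17%). The direction holds: (k − 1)/(n − 1) ≤ k/n whenever k ≤ n.

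**5. Boundaries.** If the SAP rule were used for Table 4-2, one exempted DLT would turn 1/3 Stay into 0/3 Escalate, 2/6 Stay into 1/6 Escalate, 3/6 De-escalate into 2/6 Stay, and 4/6 Unacceptable into 3/6 De-escalate. For the MTD (estimate closest to 0.30), 1/6 and 3/6 give distances 0.133 and 0.200, which selects dose 1. With 1/6 and 2/6 the distances are 0.133 and 0.033, which selects dose 2.

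**The case against.** The case for leaving this alone has four parts.

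- **Few events qualify.** A DLT must be an adverse event, and protocol 8.2.5 keeps most clinically insignificant laboratory values out of the adverse event data. What remains must be recorded, related, prolonged or severe, and still judged not clinically relevant. This stands: the frequency is probably low, and none is assumed here. The denominator example is narrower still, since a value that leads to withheld dosing will seldom be called irrelevant.
- **Safety oversight does not hang on it.** Exempted events stay in the SAP 9.6 tables of treatment-emergent, treatment-related and Grade 3 or above events. Dose level reviews also consider Grade 3 or higher toxicities that are not DLTs (protocol 11.3). Part 2 stopping uses Grade 4 or higher related events (protocol 9.4.1.1). This also stands.
- **The MTD question may not arise.** Part 1 may be eliminated (protocol 4.1), and the SAP relative dose intensity formula assumes a single 1 mg then 100 mg regimen. In that case only the reported incidence changes.
- **It is version lag.** The SAP predates Amendment 7 and differs from it elsewhere too: 100 versus 60 subjects, interval 25% to 33% versus 25% to 35%, safety follow-up at 42 versus 60 days. That may explain the conflict but does not remove it.

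A reader might infer that the SAP rule pushes the MTD upward in a known share of trials. The documents do not support that, because they give no tie-break. With 0/6 and 1/6, dose 2 is selected (distances 0.300 and 0.133). Exempt that DLT and 0/6 and 0/6 tie, so a lower-dose tie rule moves the MTD down. Enumerating a two-dose trial (cohorts of 3, Table 4-3 rates, exactly one DLT exempted at random, unsafe status held at the protocol count) gives a changed MTD in 3.3% to 12.7% of trials across tie rules. When ties go low, 2.0% (scenario 1) and 4.8% (scenario 2) move to the lower dose. Recomputing unsafe status would shift the figures again.

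**Conclusion.** The conflict is real and lies in the operative text of both documents. On the same subjects, DLT incidence under SAP 5.2 is equal to or lower than under protocol 6.2.1.2.1, never higher. The gap is 1/n for each subject whose only DLT is exempted. The direction follows from the wording alone; the expected size cannot be computed, because no event rate is given. A replacement subject enrolled after reclassification would be new data and falls outside the statement.

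Three stronger readings are not supported. No percentage or direction of MTD change is claimed, for the reasons given under the objection. It cannot be said that the SAP departed from the protocol it was written for, because the Amendment 6 text is not available. Nor can it be said that past dose level reviews used the looser rule, because neither document states which version they applied.

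Severity is minor to should-fix: a primary endpoint needs one definition, but the practical effect is probably small.

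**What to change.** Replace the DLT text in SAP 5.2 with a citation of protocol 6.2.1.2.1, or amend the protocol if the looser rule is intended. If cohorts were judged under an earlier protocol version, tabulate DLTs under that version and add one sensitivity row under the other definition. In that row, keep subjects whose dose was withheld for a protocol DLT in the denominator. The cost is SAP wording and at most one table row; no new data are needed. Protocol 9.4 calls for the SAP to be finalized before database lock, so the change fits within an update made before then.
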